5.4.6 Procedures for Randomization

Patients must not be randomized unless all eligibility criteria have been met. For Part 1 only, this includes receiving eligibility confirmation from the ICR.

Patients who satisfy all the entry criteria will be centrally assigned to study treatment by the RTSM, according to the randomization scheme generated by the designated CRO. Patients will be randomized in a 1:1 ratio to either varlitinib or placebo, both on a background of capecitabine (n=120 for Part 1 and n=350 for Part 2). The randomization scheme will be stratified by the following 2 covariates:

- Geographical region - US or ROW
- Primary tumor location – gallbladder (GB) or non-GB

The actual treatment given to patients will be determined by the randomization scheme in RTSM. The randomization scheme will be produced using SAS® version 9.4, which incorporates a standard procedure for generating randomization numbers. One randomization list will be produced containing sufficient random numbers for each of the 4 randomization strata. A blocked randomization will be generated and all centers will use the same list in order to minimize any imbalance in the number of patients assigned to each treatment group.

The dose and regimen of randomized therapy to be administered is as follows:

- Varlitinib 300 mg BID, every day
- Placebo BID, every day

Patients in both arms will receive background chemotherapy with capecitabine 1000 mg/m² BID, Day 1 to 14, followed by a 7-day rest period (21-day cycle).

Patients will be identified to the Centralized Randomization Center using site number, screening number, randomization number, gender, and date of birth. Patients will be randomized strictly sequentially within each stratum, as patients are eligible for randomization. The RTSM will inform the Investigator of the Kit ID number to be allocated to the patient at each dispensing visit via electronic data capture (EDC).

Study medication should only be dispensed to each randomized patient at the Cycle 1 Day 1 visit. It is allowed to randomize patient up to 24 hours prior to first dose. The first dose of study medication must only be administered in the morning of Cycle 1 Day 1 after pre-dose assessment (e.g., safety laboratory sampling, electrocardiogram [ECG], PK sampling) are completed. The day on which a patient takes the first dose of study medication will be considered Cycle 1 Day 1.

The Kit ID number dispensed at each visit will correspond to the treatment to which the patient was originally randomized.

If a patient discontinues participation in the study, then their screening/randomization number cannot be reused.

5.4.7 Selection of Doses in the Study

Varlitinib

The MTD of varlitinib in combination with capecitabine 1000 mg/m² BID was determined to be 400 mg BID in a previous study of the varlitinib/capecitabine combination therapy (Study ARRAY-543-204). Considering that patients with BTC who have failed one line of systemic therapy are usually frail with multiple co-morbidities, the dose of varlitinib selected for this study is 300 mg BID in combination with capecitabine. This dose combination of varlitinib and capecitabine will be assessed for safety and tolerability in the first 12 patients in the Safety lead-in, prior to randomization of patients in Parts 1 and 2 of the study.

Capecitabine

In this study capecitabine will be administered as 1000 mg/m² BID for 14 days followed by 1-week rest. Refer to [Table 5](#) for the dose calculation. Capecitabine tablets are available in 2 dosage strengths, 500mg and 150mg. In order to allow improved patient compliance and to be in line with routine clinical practice, it is allowed for patient to be dosed with ± 5% deviation from the Dose per administration (mg) listed in [Table 5](#) to reduce number of capecitabine tablets used.

The dosage, PK, and safety of capecitabine (1000 mg/m² BID, Day 1 to Day 14, followed by a 7-day rest period) have been established in the ARRAY-543-204 Phase I study. This dose of capecitabine has been successfully used with varlitinib in patients with advanced metastatic breast cancer (ASLAN001-003) and in a study (NCT00078572) conducted by Geyer, et al. where capecitabine was used in combination with lapatinib in metastatic breast cancer.¹¹ This dose of capecitabine is also supported by an article by Patt et al. 2004.¹³

Table 5: Dose Calculations for Starting Dose of Capecitabine of 1000 mg/m²

Full dose 1000 mg/m ²	Number of 150 mg tablets and/or 500 mg tablets per administration (each administration to be given morning and evening)			Reduced dose (75%) 750 mg/m ²	Reduced dose (50%) 500 mg/m ²
	Dose per administration (mg)	150 mg	500 mg		
Body Surface Area (m ²)				Dose per administration (mg)	Dose per administration (mg)
≤1.26	1150	1	2	800	600
1.27 - 1.38	1300	2	2	1000	600
1.39 - 1.52	1450	3	2	1100	750
1.53 - 1.66	1600	4	2	1200	800
1.67 - 1.78	1750	5	2	1300	800
1.79 - 1.92	1800	2	3	1400	900
1.93 - 2.06	2000	-	4	1500	1000
2.07 - 2.18	2150	1	4	1600	1050
≥ 2.19	2300	2	4	1750	1100

5.4.8 Selection and Timing of Dose for Each Patient

Safety Lead-in

Varlitinib will be administered BID with a meal or within 30 minutes after food intake, approximately at the same time (± 2 hours), in the morning and evening each day, using the appropriate number of 100 mg tablets. High fat meal should be avoided and varlitinib tablets should not be chewed, crushed, or broken.

On Cycle 1 Day 1, Cycle 1 Day 8, and Cycle 1 Day 14, varlitinib tablets (morning dose) can only be administered under the supervision of the Investigator (or designee).

Capecitabine will be administered with food at the same time as varlitinib BID for 14 days with 7 days rest in a 21-day cycle.

A sample low fat meal is:

Food Item	Calories (kcal)	Fat (g)	Carbohydrate (g)	Protein (g)
2 slices of white bread toast	134	1.7	25	3.8
1 tablespoon light fat margarine*	59	6.6	Trace	Trace
1 tablespoon jelly	55	Trace	14	Trace
8 fluid ounces of skim milk	86	0.4	11.8	8.4
Total calories (kcal)	334	78	206	50
% of total calories	100	23	62	15

* Margarine spread: approximately 48% fat. Source: USDA National Nutrient Database for Standard reference, 2010

*Type of low fat meal to be given with varlitinib should be based on the investigator's judgement

During the Cycle 1 Day 1 and Day 8 visits, the morning meal will be a small snack to be taken approximately 30 minutes prior to morning dosing of varlitinib. Patients will remain fasted until after the 6-hour ECG/PK assessment when they will receive a snack/small meal. The next meal can be taken after the 8.5-hour ECG/PK assessment. Timing and type of meal will be recorded on the CRF.

Part 1 and 2

Varlitinib or placebo will be administered BID with a meal or within 30 minutes after food intake, approximately at the same time (± 2 hours), in the morning and evening each day, using the appropriate number of 100 mg tablets. High fat meal should be avoided and varlitinib tablets should not be chewed, crushed or broken.

Retake of one dose of varlitinib or placebo is allowed if patient vomits within 30 minutes after administration of varlitinib or placebo. Retaking of varlitinib is not allowed if patient vomits again upon first retake.

On Cycle 1 Day 1 and Cycle 1 Day 8 (Part 1 only), Cycle 2 Day 1, varlitinib tablets (morning dose) can only be administered under the supervision of the Investigator (or designee).

Capecitabine will be administered with food at the same time as varlitinib or placebo BID for 14 days with 7 days rest in a 21-day cycle. Dose modification details are provided in [Section 5.4.8.1](#).

Study medication will be dispensed to each patient to take at home after leaving the study center until the next scheduled visit. The study medication is to be taken until the patient

experiences an unacceptable toxicity, withdraws consent, disease progression (as assessed by the Investigator based on RECIST version 1.1 [[Appendix 14.1](#)]), or death.

5.4.8.1 Dose Modification

If a patient experiences a clinically significant adverse event of CTCAE 4.03 Grade 3 and above, not attributable to the disease or disease-related processes under investigation, dosing of investigational product and/or background therapy will be interrupted or the dose reduced and supportive therapy administered as required*. Any change in study medication needs to be recorded in the CRFs along with the reason for the change.

*Note: In the Safety lead-in, treatment will continue for a minimum of 14 days, during which time dose adjustment is not allowed. Dose adjustment and interruption is allowed from Day 15 onwards.

The recommended dose adjustment schedule for the investigational product (varlitinib/placebo) and capecitabine are described in [Table 6](#) and [Table 7](#) below, respectively, with the exception of hyperbilirubinemia, as well as serum creatinine increase, which are described separately in [Section 5.4.8.2](#). Clinical judgment of the treating investigator should guide the management plan for each patient based on individual benefit/risk assessments.

Table 6: Recommended Dose Adjustments for Varlitinib/Placebo

Toxicity (NCI CTCAE 4.03 Grades)	During a Course of Therapy	Dose Adjustment for Next Treatment
Grade 1 and 2	Maintain dose level	Maintain dose level
Grade 3 and above		
1st appearance	Interrupt until resolved to grade 0-2	300 mg BID
2nd appearance		200 mg BID
3rd appearance		100 mg BID
4th appearance	Discontinue treatment permanently	-

Abbreviations: BID = twice daily, NCI CTCAE = The National Cancer Institute Common Terminology Criteria for Adverse Events.

Table 7: Recommended Dose Adjustment for Capecitabine

Toxicity (NCI CTCAE 4.03 Grades)	During a Course of Therapy	Dose Adjustment for Next Treatment
Grade 1	Maintain dose level	Maintain dose level
Grade 2		
1st appearance	Interrupt until resolved to grade 0-1	1000 mg/m ²
2nd appearance		750 mg/m ²
3rd appearance		500 mg/m ²
4th appearance	Discontinue treatment permanently	-
Grade 3		
1st appearance	Interrupt until resolved to grade 0-1	750 mg/m ²
2nd appearance		500 mg/m ²
3rd appearance	Discontinue treatment permanently	-
Grade 4		
1st appearance	Discontinue permanently OR If physician deems it to be in the patient's best interest to continue, interrupt until resolved to Grade 0-1	500 mg/m ²

Abbreviation: NCI CTCAE = The National Cancer Institute Common Terminology Criteria for Adverse Events.

Any interruption in dose or reduction in dose of study medication and background therapy needs to be captured in the CRF. In the event that the administration of varlitinib/placebo or capecitabine is interrupted for longer than 6 consecutive weeks, varlitinib/placebo or capecitabine must be permanently withdrawn. If capecitabine is permanently withdrawn, patients are allowed to continue in the study on varlitinib/placebo until disease progression, unacceptable toxicity, withdrawal of consent, or death. Similarly, in the event that varlitinib/placebo is permanently withdrawn, patients are allowed to continue

in the study on capecitabine until disease progression, unacceptable toxicity, withdrawal of consent, or death.

5.4.8.2 Management of Toxicities

Management of Gastrointestinal Toxicities attributable to Varlitinib

Diarrhea:

For the management of diarrhea for patients in this study, routine loperamide prophylaxis as a standby is recommended. The recommend dose of loperamide is 2 mg three times a day (TID). Buscopan or a similar antispasmodic agent is recommended for management of acute symptoms. The recommended initial dose of Buscopan is 20 mg TID and can be escalated to 20 mg QID.

The pharmacologic interventions for treatment emergent diarrhea should include:

First line therapy – loperamide

- If receiving routine loperamide prophylaxis, increase dose to a maximum of 16 mg/day.
- If new-onset diarrhea, take loperamide 4 mg with first bout of diarrhea followed by 2 mg every 4 hours or after every unformed stool (maximum 16 mg/day). Continue until diarrhea-free for 12 hours.
- With recovery to \leq Grade 1, take loperamide 2 mg TID.

As a second line therapy for the treatment of diarrhea refer to [Table 8](#).

Table 8: Recommended Management of Diarrhea Attributable to Varlitinib

Toxicity (NCI CTCAE 4.03 Grades)	Treatment	Dose Adjustment
Grade 1	If persistent diarrhea on loperamide, add diphenoxylate hydrochloride plus atropine sulfate (Lomotil®) 2.5 mg every 6 to 8 hours	Maintain dose level
Grade 2	If persistent diarrhea on loperamide, add octreotide (short acting) 150 µg SC TID, or after the initial dose of short acting octreotide, if well tolerated, a single dose of octreotide LAR 20 mg intramuscularly	Maintain dose level
Grade 3 or Grade 4	after intensive loperamide therapy, titrate loperamide to keep diarrhea controlled (< 4 stools/day)	1st occurrence Maintain dose level
	Octreotide (100 to 150 µg SC BID or 25 to 50 µg/hour IV if dehydration is severe, with dose escalation up to 500 µg SC TID	2nd occurrence Reduce Varlitinib/placebo dose to 200 mg BID
	IV fluids as appropriate	3rd or more occurrence
	consider prophylactic antibiotics, especially if diarrhea is persistent beyond 24 hours or if there is a fever or Grade 3 /4 neutropenia	Reduce Varlitinib/placebo dose to 100 mg BID

Abbreviations: BID = twice daily, IV = intravenous, NCI CTCAE = The National Cancer Institute Common Terminology Criteria for Adverse Events, SC = subcutaneous, TID = 3 times a day.

Nausea/Vomiting:

Both varlitinib and capecitabine are considered to have low to minimal emetic risk. Routine prophylaxis for nausea/vomiting is not recommended. Anti-emetic medications can be used on an as-needed basis (PRN). If nausea/vomiting recur in later cycles of treatment, prophylactic medications can be used on the discretion of Investigator. Several anti-emetic drugs have QT prolongation effects and therefore are not allowed in the Safety lead-in part of this study, which will assess the QTc prolongation effect of study medications. The recommended management of nausea/vomiting is listed in [Table 9](#).

*Metoclopramide, dolasetron, granisetron, and ondansetron are prohibited in the Safety lead-in (Cycle 1 Day 1 to Cycle 2 Day 1) and Part 1 (Cycle 1 Day 1 to Cycle 2 Day 1) of this study due to their QT prolonging effect. These medications can be used with caution in Part 2 of this study ([Section 5.4.10](#)). From Cycle 2 Day 2 in the Safety lead-in and Part 1 of this study and in the event that symptoms cannot be controlled by panolsetron or patients are intolerant to panolsetron, then investigators are allowed to prescribe metoclopramide, dolasetron, granisetron, and ondansetron without prior approval. However for tracking purpose, Sponsor must be informed if the above medications have been used.

Table 9: Recommended Management of Nausea/Vomiting attributable to Varlitinib

Study part	Breakthrough treatment for acute symptom control	Prophylaxis for recurrent nausea/vomiting (start 30 mins before study treatment)
Safety lead-in Part1 (Cycle 1 Day 1 to Cycle 2 Day 1)	Olanzapine 5-10 mg PO QD PRN or Prochlorperazine: 5-10 mg every 6 hours PRN (maximum 40 mg/day)	Prochlorperazine: 10 mg PO and then every 6 hours PRN (maximum 40 mg/day) or Palonsetron: 0.25 mg IV every 5 days
Part 1 (Cycle 2 Day 2 and afterward) and Part 2	Olanzapine 5-10 mg PO QD PRN or Prochlorperazine: 5-10 mg every 6 hours PRN (maximum 40mg/day) or Metoclopramide: 10-20 mg PO/IV every 4-6 hours PRN or Dexamethasone 12 mg PO/IV and QD PRN* or Haloperidol 0.5-2 mg PO/IV every 4-6 hours Or one of the following: Dolasetron: 100 mg PO QD PRN Granisetron: 1-2 mg (total dose) PO QD PRN or 1 mg PO BID PRN or 1 mg IV QD PRN or 3.1 mg/24 hours transdermal patch every 7 days Ondansetron: 16-24 mg PO QD PRN or 8-16 mg IV QD PRN	Metoclopramide: 10-20 mg PO and then every 6 h PRN or Prochlorperazine: 10 mg PO and then every 6 hours PRN (maximum 40 mg/day) or one of the following: Dolasetron: 100 mg PO QD PRN Granisetron: 1-2 mg PO QD PRN or 3.1 mg/24 hours transdermal patch every 7 days Ondansetron: 8-16 mg PO QD PRN Palonsetron: 0.25 mg IV every 5 days

Abbreviations: BID = twice daily, IV = intravenous, PO = per oral, PRN = as needed, QD = once daily.

Taken from NCCN Guidelines version 1.2017: Antiemesis.

*: moderate CYP3A4 inhibitor, use with caution.

Management of hyperbilirubinemia and serum creatinine attributable to Varlitinib

Hyperbilirubinemia

The dose adjustment schedule for investigational product (varlitinib/placebo) when hyperbilirubinemia occurs in combination with an increase in transaminases (ALT, AST) of CTCAE 4.03 Grade 2 and above is described in [Table 10](#).

Table 10: Recommended Dose Adjustment for Management of Hyperbilirubinemia with Increased Transaminases

Toxicity (NCI CTCAE 4.03 Grades)	During a Course of Therapy	Dose Adjustment for Next Treatment
Grade 1	Maintain dose level	Maintain dose level
Grade 2 and 3		
1st appearance	Interrupt until resolved to grade 0-1	300 mg BID
2nd appearance		200 mg BID
3rd appearance		100 mg BID
4th appearance	Discontinue treatment permanently	-
Grade 4		
1st appearance	Interrupt until resolved to grade 0-1	200 mg BID
2nd appearance	Interrupt until resolved to grade 0-1	100 mg BID
3rd appearance	Discontinue treatment permanently	-

Abbreviations: BID = twice daily, NCI CTCAE = The National Cancer Institute Common Terminology Criteria for Adverse Events.

If hyperbilirubinemia is primarily due to an increase in indirect bilirubin (with indirect bilirubin > direct bilirubin and direct bilirubin $\leq 1.5 \times$ ULN) with no increase in transaminases levels (ALT, AST) or an increase in transaminases of \leq Grade 1, follow the dose adjustment schedule in [Table 11](#).

Table 11: Recommended Dose Adjustment for Management of Hyperbilirubinemia due to Indirect Bilirubin

Toxicity (NCI CTCAE 4.03 Grades)	During a Course of Therapy	Dose Adjustment for Next Treatment
Grade 1 and 2	Maintain dose level	Maintain dose level
Grade 3 and above		
1st appearance	Interrupt until resolved to grade 0-2	300 mg BID
2nd appearance		200 mg BID
3rd appearance		100 mg BID
4th appearance	Discontinue treatment permanently	-

Abbreviations: BID = twice daily, NCI CTCAE = The National Cancer Institute Common Terminology Criteria for Adverse Events.

Increased Serum creatinine

Dose adjustment schedule for investigational product (varlitinib/placebo) as a result of increased serum creatinine levels is described in the [Table 12](#).

Table 12: Recommended Dose Adjustment for Management of Increase Serum Creatinine

Toxicity (NCI CTCAE 4.03 Grades)	During a Course of Therapy	Dose Adjustment for Next Treatment
Grade 1	Maintain dose level	Maintain dose level
Grade 2 and 3		
1st appearance	Interrupt until resolved to grade 0-1	300 mg BID
2nd appearance		200 mg BID
3rd appearance		100 mg BID
4th appearance	Discontinue treatment permanently	-
Grade 4		
1st appearance	Interrupt until resolved to grade 0-1	200 mg BID
2nd appearance	Interrupt until resolved to grade 0-1	100 mg BID
3rd appearance	Discontinue treatment permanently	-

Abbreviations: BID = twice daily, NCI CTCAE = The National Cancer Institute Common Terminology Criteria for Adverse Events.

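### Grade 3–4 diarrhea falls under both Table 6 and Table 8 with no precedence stated; the tables contradict each other at the fourth event and are inconsistent on interruption at the first

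*Protocol*

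**What the plan says.** Protocol Section 5.4.8.1 sets a general rule for clinically significant adverse events of Grade 3 or above that are not due to the disease: "dosing of investigational product and/or background therapy will be interrupted or the dose reduced", with supportive therapy as needed. It then sends varlitinib/placebo adjustments to Table 6 and capecitabine adjustments to Table 7, "with the exception of hyperbilirubinemia, as well as serum creatinine increase, which are described separately in" Section 5.4.8.2. Diarrhea is not among the exceptions. The same section calls the schedules recommended and leaves each patient's management to the investigator's judgment.

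For Grade 3 and above, Table 6 says "Interrupt until resolved to grade 0-2" at the first appearance. The next dose is 300, 200 and 100 mg BID after the first, second and third appearances. At the fourth it says "Discontinue treatment permanently".

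Table 8 in Section 5.4.8.2 covers diarrhea attributable to varlitinib and has its own dose column. For Grade 3 or 4 it reads "1st occurrence Maintain dose level". At the second occurrence it says "Reduce Varlitinib/placebo dose to 200 mg BID". For the "3rd or more occurrence" it says "Reduce Varlitinib/placebo dose to 100 mg BID".

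Protocol Section 3.2.2 reports that diarrhea, nausea and vomiting were frequent across the varlitinib studies. It gives no rate by grade.

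**The concern.** A Grade 3–4 diarrhea episode meets the entry condition of both tables, and the protocol does not rank them. A site that opens Table 6 and a site that opens Table 8 could take different actions for the same patient history. One difference is whether dosing is interrupted at the first episode. The other is whether the patient stays on treatment after the fourth.

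This is first a matter of clear instructions to sites on a foreseeable toxicity. It also reaches the analysis:

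- Whether an interruption starts has consequences of its own. Section 5.4.8.1 requires permanent withdrawal of a drug interrupted for more than 6 consecutive weeks, and Section 5.4.11 leaves doses withheld for Grade 3 or higher events out of the compliance count.
- SAP Section 3.2.2 subtracts interruptions from exposure and builds both dose-intensity measures from the dose delivered. SAP Section 7.7.5 summarizes these by arm.
- SAP Section 7.7.1 tabulates adverse events leading to discontinuation by arm.

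**Working it through.** No sample size, power or error rate is involved, so the check is a comparison of the texts.

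**Step 1: do both tables apply?** The exception clause in Section 5.4.8.1 names two toxicities, each with its own schedule in Section 5.4.8.2 (Tables 10 to 12). Diarrhea also has a schedule there but is not named. Nausea and vomiting raise no similar problem, because Table 9 has no dose column for study drug. On the text, diarrhea is the one toxicity with a dose schedule in Section 5.4.8.2 that has not been taken out of Table 6.

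**Step 2: compare the steps for Grade 3–4 diarrhea.**

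| Event | Table 6 | Table 8 | Result |
|---|---|---|---|
| 1st | Interrupt to Grade 0–2, then 300 mg BID | Dose unchanged (300 mg BID) | Same dose level; inconsistent on interruption |
| 2nd | 200 mg BID | 200 mg BID | Same dose level; Table 8 silent on interruption |
| 3rd | 100 mg BID | 100 mg BID | Same dose level; Table 8 silent on interruption |
| 4th | Permanent stop | 100 mg BID | Direct contradiction |

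Two cautions on layout. In the text as extracted, Table 6's interruption wording stands only in the first-appearance row. It probably spans the second and third rows as a merged cell, but that is an inference. Also, Table 6 separates action during the course from the dose for the next treatment, whereas Table 8 has a single dose column. At events 2 and 3, then, Table 8 only omits interruption, and I do not count that as a conflict.

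**Step 3: is the first event only silence too?** Not quite. In its during-course column, Table 6 uses the same phrase about maintaining the dose for Grades 1 and 2, as the alternative to interrupting. The general rule in Section 5.4.8.1 also calls for interruption or reduction when a Grade 3 or higher event is clinically significant. Table 8's first step states neither.

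**Step 4: what would the SAP's measures record?**

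- *First event.* Actual exposure = intended exposure − days of interruption. A patient interrupted for k days loses k days of actual exposure; a patient whose dose is kept loses none. Both are then at 300 mg BID.
- *After a fourth event, until progression.* Under Table 8 the patient receives 100/300 = 33% of the intended dose, assuming no missed doses. Under Table 6 the patient receives 0/300 = 0%.
- *Percentage of intended dose* runs to progression, so this period enters at 33% or at 0%.
- *Relative dose intensity* runs to the earlier of discontinuation and progression. The period enters at 33% under Table 8 and drops out under Table 6. If the patient's relative dose intensity up to that point was above one third, following Table 8 lowers it and following Table 6 does not.

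For identical toxicity, the two measures can therefore move in opposite directions depending on the table used. In addition, only the Table 6 path records a discontinuation at that event.

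**The case against.** The strongest reply is that a specific table overrides a general one. Table 8 is confined to diarrhea attributable to varlitinib, is introduced as second-line management after loperamide, and sits in the section to which the exceptions point. That reading is natural. But the protocol does not state it, and an exception clause that names two other toxicities points the other way.

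A second reply is that the tables can be read together. This works for the dose levels at events 1 to 3. It might work for the first event as well: interrupt, then resume at the unchanged level. It cannot work for the fourth event.

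A third is that both tables are recommendations under clinical judgment. This stands to the extent that a site following one table does not breach the other. The deviations named in SAP Sections 5.1 and 5.2 do not include departures from these tables. But judgment governs departures from a default, and here there are two defaults.

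A fourth is that stopping is covered elsewhere. Section 5.3.4 stops therapy when clinically significant symptoms are not controlled by standard treatment, and Section 5.4.11 allows temporary or permanent interruption for Grade 3 or higher events. So Table 8 does not oblige a patient to continue through uncontrolled diarrhea. These clauses do not replace Table 6's stop at a fourth event, and they do not say which table applies.

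**Conclusion.** The plan is wrong as written on this point. Of four steps, one is a direct contradiction (the fourth event), one is inconsistent on interruption (the first), and two agree on dose with Table 8 silent on interruption. The conclusion rests on taking the exception clause at its word and on the extracted table layout described above.

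Three stronger readings are tempting but unsupported:

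- *That the tables give opposite instructions throughout.* The dose levels agree at events 1 to 3.
- *That this is the drug's most frequent toxicity.* Protocol Section 3.2.2 lists diarrhea with nausea and vomiting, ranks none of them, and says most episodes were managed with standard medication. The rate of Grade 3–4 diarrhea, and of a fourth such episode in one patient, is not given, so the number of patients affected cannot be estimated.
- *That the problem falls mainly on the varlitinib arm or biases the primary result.* An imbalance between arms is a plausible inference from a drug-related toxicity, but the documents give no comparative rates. The primary efficacy analyses use all randomized patients as assigned, and PFS events count regardless of withdrawal from therapy. The inconsistency therefore does not alter who is analyzed or what counts as an event. The direct effect is on consistency of patient management and on the tolerability summaries.

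**What to change.** Reconcile Table 6 with Table 8. State in Section 5.4.8.1 which table governs Grade 3–4 diarrhea attributable to varlitinib. If it is Table 8, add diarrhea to the exception clause; if it is Table 6, align or remove the dose column in Table 8. Either way, say explicitly whether dosing is interrupted at each event and what happens at the fourth, and cross-refer to Sections 5.3.4 and 5.4.11 so that one event leads to one action. Which clinical rule to adopt is the sponsor's decision, and this review takes no view on it.

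The cost is one clarifying amendment or letter to sites. It needs no new data and no change to the sample size or the SAP's formulas.

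### Table 10 does not name the analyte that selects its row; read by bilirubin grade, it conflicts with Table 6 when bilirubin is Grade 1 and ALT/AST is Grade 3 or 4

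*Protocol*

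**What the plan says.** All references are to the protocol; the SAP does not address these dosing rules.

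- **General rule (5.4.8.1).** It opens: "If a patient experiences a clinically significant adverse event of CTCAE 4.03 Grade 3 and above, not attributable to the disease". The action is that "dosing of investigational product and/or background therapy will be interrupted or the dose reduced".
- **Table 6 (5.4.8.1), "Recommended Dose Adjustments for Varlitinib/Placebo".** Grades 1 and 2: keep the dose. Grade 3 and above: interrupt until Grade 0-2, then restart at 300, 200 or 100 mg BID after the first, second or third appearance, and stop for good at the fourth.
- **Exemption (5.4.8.1).** The Table 6 and Table 7 schedules apply "with the exception of hyperbilirubinemia, as well as serum creatinine increase, which are described separately in" Section 5.4.8.2. Transaminase elevation is not named in the exemption.
- **Table 10 (5.4.8.2), "Recommended Dose Adjustment for Management of Hyperbilirubinemia with Increased Transaminases".** It applies when "hyperbilirubinemia occurs in combination with an increase in transaminases (ALT, AST) of CTCAE 4.03 Grade 2 and above". Grade 1: keep the dose. Grades 2 and 3: "Interrupt until resolved to grade 0-1", then 300, 200 or 100 mg BID by appearance, with a permanent stop at the fourth. Grade 4: the same interruption rule, then 200 or 100 mg BID, with a permanent stop at the third.
- **Table 11 (5.4.8.2).** It covers mainly indirect hyperbilirubinemia with ALT/AST normal or at most Grade 1. Its rows run up to Grade 3 and above.
- **Status of the tables (5.4.8.1).** "Clinical judgment of the treating investigator should guide the management plan for each patient based on individual benefit/risk assessments".

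**The concern.** Two abnormalities bring a patient into Table 10, but its row labels and its resolution rule name neither. If the row is chosen by bilirubin, the Grade 1 row covers a patient whose ALT/AST is at Grade 3 or 4, and that row leaves varlitinib unchanged.

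The result runs the wrong way. ALT/AST at Grade 3 with normal bilirubin falls under Table 6 and is interrupted. Add a Grade 1 bilirubin rise and the patient enters Table 10, which says to carry on. The worse liver picture gets the looser instruction.

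What is at stake is consistent handling of a liver-safety event. Section 3.2.2 reports that raised transaminases and hyperbilirubinemia have both been seen with varlitinib. Table 2 adds liver tests at Cycle 1 Days 8 and 15, so sites will have both results and will need one rule. Two sites following the protocol in good faith could treat the same patient differently.

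**Working it through.** The plan gives no figure to reproduce. The check sets the tables side by side over every grade combination that can enter Table 10.

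**Step 1: which analyte?** Table 11 admits only patients with ALT/AST at Grade 1 or below, yet its rows reach Grade 3 and above, so they can only be bilirubin grades. Table 10 has the same column label, sits under the same hyperbilirubinemia sub-heading, and has a title in which bilirubin is the toxicity and transaminases qualify it. Reading both tables by bilirubin is natural.

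The Table 10 rows reached under each possible reading are:

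- bilirubin grade: 1, 2, 3, 4
- ALT/AST grade: 2, 3, 4 (entry requires at least Grade 2, so the Grade 1 row could never be used)
- higher of the two: 2, 3, 4 (same consequence)
- lower of the two: 1, 2, 3, 4

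**Step 2: the grid.** Bilirubin Grade 1-4 by ALT/AST Grade 2-4 gives 4 x 3 = 12 combinations. Table 10 is read by bilirubin grade and Table 6 by ALT/AST grade.

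| Bilirubin | ALT/AST 2 | ALT/AST 3 | ALT/AST 4 |
|---|---|---|---|
| 1 | both keep dose | **T10 keeps, T6 interrupts** | **T10 keeps, T6 interrupts** |
| 2 | T10 interrupts, T6 keeps | both interrupt | both interrupt |
| 3 | T10 interrupts, T6 keeps | both interrupt | both interrupt |
| 4 | T10 interrupts, T6 keeps | both interrupt | both interrupt |

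Count: 1 (same, keep) + 2 (conflict) + 3 (Table 10 stricter) + 6 (both interrupt) = 12. The 3 stricter cells are not counted as conflicts, because Table 10 exists to add a bilirubin-driven action there.

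**Step 3: does the choice of reading matter?** Cells where Table 10 keeps the dose while Table 6 interrupts: bilirubin reading 2, lower-of-two reading 2 (the same cells), ALT/AST reading 0, higher-of-two reading 0.

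**Step 4: what differs in the 2 cells.** At first appearance, Table 6 interrupts and then restarts at 300 mg BID, so the difference is the interruption and not the restart dose. On recurrence Table 6 steps to 200 mg, then 100 mg, then a permanent stop. The Grade 1 row of Table 10 has no appearance count, so it never steps down.

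**Step 5: restart.** In the 6 cells where both tables interrupt, Table 10 asks for Grade 0-1 and Table 6 for Grade 0-2. Read by bilirubin, Table 10's condition could be met while ALT/AST is still Grade 3 or above. That Table 6 must also be satisfied is nowhere stated.

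**The case against.** The best reply is that nothing conflicts. The exemption from Table 6 names hyperbilirubinemia and creatinine, not transaminases, so a Grade 3-4 ALT/AST rise is still a Table 6 event. An investigator who applies both tables finds no bilirubin-driven change in Table 10, finds an interruption in Table 6, and interrupts. The general rule points the same way: this part of 5.4.8.2 covers events attributed to varlitinib, so meeting that rule by holding only capecitabine would be strained. The tables are recommendations, and judgment guides management.

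Much of this stands. It is a sensible way to read the protocol, and it is the reading the fix below would write down. But the protocol does not state it. Table 10 is presented as the schedule for exactly this combined event, and a site may as easily conclude that the hyperbilirubinemia exemption takes the whole event out of Table 6. The general rule is limited to clinically significant events and allows reduction as well as interruption, so it does not settle which table governs.

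A reader might infer that the protocol keeps patients at full dose through severe transaminase rises. The documents do not support that: it requires Table 10 to displace Table 6 for ALT/AST, which no sentence says. A reader might also infer that the bilirubin reading is the only one that uses the Grade 1 row. It is the only single-analyte reading that does; a lower-of-two reading reaches the row as well, with the same two conflicts.

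**Conclusion.** Wrong as written: two dosing rules give opposite instructions for bilirubin Grade 1 with ALT/AST Grade 3 or 4, and no text ranks them. The size is 2 of 12 grade combinations. That counts cells, not patients, and the documents give no frequency for the pattern. No endpoint, power or alpha is affected.

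The conclusion assumes that Table 10 is read by bilirubin grade, as Table 11 must be. It concerns only events attributed to varlitinib. Entry allows controlled biliary obstruction and ALT/AST up to 5 x ULN, so attribution will keep some cases out. In the Safety lead-in, doses cannot be adjusted in the first 14 days.

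Three further claims are tempting but not supported:

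- *Table 10 is ambiguous in 7 of 12 combinations.* That is the number of cells where the bilirubin and ALT/AST readings pick different rows. It gives equal weight to a reading that leaves the Grade 1 row unusable and breaks with Table 11.
- *The row should follow the higher of the two grades, or both analytes must reach Grade 0-1.* These are clinical choices. The first would interrupt bilirubin Grade 1 with ALT/AST Grade 2, where both tables now keep the dose. The second is stricter on ALT/AST than Table 6. The documents do not show that either is needed.
- *Direct-predominant hyperbilirubinemia with ALT/AST at Grade 1 or below is a second contradiction.* It meets the entry condition of neither Table 10 nor Table 11, but no two rules clash. It is missing detail, with the general Grade 3+ rule and clinical judgment still available.

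**What to change.** Add to 5.4.8.2, at Table 10, a statement that:

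1. the row is selected by the bilirubin grade;
2. Table 6 continues to apply to the ALT/AST grade;
3. when both apply, the more conservative instruction governs;
4. varlitinib/placebo restarts only when bilirubin meets Table 10 (Grade 0-1) and ALT/AST meets Table 6 (Grade 0-2).

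This takes the 2 conflicting cells to 0: both become an interruption until ALT/AST is at Grade 0-2, with bilirubin already within Grade 0-1. Bilirubin Grade 1 with ALT/AST Grade 2 still keeps the dose. The 3 cells where Table 10 is stricter are unchanged in action, and the 6 cells where both interrupt gain a stated restart condition.

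The cost is a few sentences and no new data: total and direct bilirubin, ALT and AST are already in the chemistry panel and the extra Cycle 1 liver tests. The one downside is that some interruptions may be longer, which counts against the rule in 5.4.8.1 that more than 6 consecutive weeks off drug means permanent withdrawal.
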